#### **1 Introduction**

This document is a protocol for a human research study. This study is to be conducted according to US and international standards of Good Clinical Practice (International Conference on Harmonization ICHE6), the Code of Federal Regulations Title 21 parts 803 and 812, and other applicable government regulations and Institutional research policies and procedures.

#### **1.1 Background/Significance**

The vagus nerve (VN) provides a bidirectional link between the brain and the gastrointestinal tract, and as such, is involved in maintaining the homeostasis of gut functions such as sensitivity, motility, and immunity both through its sensing and modulatory roles (Matteoli & Boeckxstaens 2013). The VN classically innervates the digestive tract from the esophagus to the splenic flexure, however for some anatomists, the VN innervates all the digestive tract in human. Dysfunction of the vagal tone has been observed in functional and inflammatory digestive disorders (Bonaz et al 2016 Rev). Being a major component in the control of upper gastrointestinal motility, low vagal tone has been associated with gastrointestinal motility disturbances (Bonaz et al 2016 Rev).

Gastroparesis is a disorder associated with delayed gastric emptying in the absence of mechanical obstruction. Patients with gastroparesis are often malnourished and experience a range of symptoms from nausea, vomiting, postprandial fullness, early satiety, and abdominal pain leading to significantly compromised quality of life and economic burden (Wang et al 2008; Talley et al 2001). Implicated etiologic factors include diabetes mellitus, although a third of the cases are idiopathic. Physiological vagal input to cholinergic enteric neurons is necessary to maintain a basal gastric tone and is important for gastric accommodation in humans (Lunding et al 2008; Azpiroz & Malagelada 1987). Antral dysmotility is a consistent finding in diabetics with delayed gastric emptying and impaired gastric autonomic innervation probably contributes to this dysmotility. An additional layer of complexity is provided by the fact that the digestive tract is exposed to a variety of luminal signals derived from the microbiota (Guarino et al 2016). Beyond the well-documented effects on gut immune responses, recent data suggest that dysbiosis of gut microbiota can affect gastrointestinal motility (Guarino et al 2016), although this has not been studied in gastroparesis.

Inflammation is increasingly recognized as playing an important role in gastrointestinal motility disorders such as gastroparesis (Spiller & Major 2016). Immune

cells such as macrophages and mast cells are found in close proximity to neurons within the enteric nervous system (Gabanyi et al 2015). Alterations in inflammatory mediators such as cytokines and number of leukocytes are found in gastroparesis and other gastrointestinal motility disturbances (Spiller & Major 2016). Moreover, leukocytes release mediators (e.g. cytokines, neurotransmitters) that alter neuronal activity and have been termed “neuroimmune synapse” leading to pro- and anti-inflammatory neural reflexes (Franco et al 2007). In addition, immune cells express receptors for neurotransmitters, including dopamine, acetylcholine, and norepinephrine, which can regulate leukocyte activity and differentiation. Thus neuroimmune interaction is a bidirectional process important in health and disease, particularly if inflammation is implicated (Franco et al 2007).

The VN is a major constituent of a neural reflex mechanism—the inflammatory reflex—that controls innate immune responses and inflammation during pathogen invasion and tissue injury. VN anti-inflammatory properties are mediated through the activation of the hypothalamic–pituitary–adrenal axis (HPA) by its afferents and by activating the cholinergic anti-inflammatory pathway locally through its efferents (rev by Tracy 2016). VN stimulation (VNS) has potent anti-inflammatory effects (Zhao et al 2012; Cialotto et al 2014) and can improve colitis in rats (Meregnani et al 2011; Ji et al 2014). In a small study with healthy volunteers, it was demonstrated that transcutaneous VNS enhances gastric motility and reduces somatic pain sensitivity (Frøkjaer et al 2016). VNS has further been shown to induce a clinical, biological, and endoscopic remission at 6 months in small cohorts of patients with active Crohn’s disease (Bonaz et al 2016, Haens et a. 2016). However, VNS mechanisms of anti-inflammatory responses in the gut have not been established, nor described in detail. Further investigations are needed to explore the intestinal component of digestive tract inflammation and motility under the modulation of vagal tone reinforcement.

Given that autonomic dysfunction has been frequently reported in patients with gastrointestinal motility disorders and inflammatory bowel disease, ***the central hypothesis*** of our project is that improving vagal tone can have pro-kinetic and anti-inflammatory effects of clinical relevance. We further ***hypothesize*** that gastroparesis is associated with improper immune interactions and microbial dysbiosis leading to disruption of neuronal function. In addition to supportive measures (e.g. dietary changes, glycemic control) and symptomatic control (e.g. anti-emetics), active treatment with pharmacologic agents and vagal/electrical stimulators has led to variable efficacy. Detailed molecular and neuroimmune studies are likely to identify patient heterogeneity and those that are likely to benefit from specific therapies – “precision medicine”. Thus with these in mind we propose the following specific aims (see below).

## 1.2 Specific Study Aims

Study Aim 1: Investigate molecular and neuroimmune signaling pathways in gastroparesis patients prior to treatment as compared to non-gastroparesis controls.

Study Aim 2: Investigate molecular and neuroimmune signaling pathways in gastroparesis patients post-treatment with VNS, and compared to pre-treatment.

Study Aim 3: Define microbial features and investigate microbial dysbiosis associated with gastroparesis.

## **2 Innovation**

The etiology and pathophysiology of gastroparesis remains enigmatic despite evidence of underlying inflammation and dysautonomia. Additionally, therapies for delayed gastric emptying and its associated symptoms are limited. Given its extensive innervation of the stomach and its predominant role in parasympathetic regulation of inflammation and motility, the VN may be utilized as a powerful therapeutic target. As such, we are proposing to use VNS to induce pro-kinetic and anti-inflammatory changes of clinical relevance. Although gastric pacemakers are available as therapy for medically-refractory gastroparesis, these devices require surgery and have not demonstrated significant pro-kinetic effects (Ross et al, 2014; Yin et al 2012). VNS appears to be safe, well tolerated, and effective in the treatment of other inflammatory disorders with associated dysautonomia, such as rheumatoid arthritis (Koopman et al 2016) and Crohns disease (Bonaz et al 2016, Haens et a. 2016). The therapeutic effect of VNS in these disorders is based on stimulation of the cholinergic anti-inflammatory pathway (Tracy 2009; Howland 2014), which specifically targets pro-inflammatory macrophages in the myenteric plexus (Matteoli et al 2013), which have been implicated in the pathogenesis of gastroparesis. As such, VNS could potentially act as a disease modifier in gastroparesis. There are no therapies to date that have the potential to reverse underlying pathologic abnormalities in gastroparesis. VNS, through its anti-inflammatory and pro-kinetic effects, may offer a safe and well tolerated therapy for treatment of gastroparesis. In this study we propose establishing proof of concept for a novel therapy for gastroparesis. Additionally, we will attempt to fill the large gaps in pathophysiology of this disease by a detailed study of the neuro-immune interactions in patients with gastroparesis.

## **3 Study Design**

### **3.1 General Design**

This is a prospective interventional pilot study assessing the safety and tolerability, as well as efficacy of the use of VNS in patients with idiopathic and functional gastroparesis. We will also include patients with functional dyspepsia, which have almost identical clinical symptomatology and are believed to share similar underlying inflammation and dysautonomia. We plan to recruit a total of 45 patients, 15 patients of each subgroup, for 4 weeks of therapy with VNS. Patients will undergo baseline measures of symptoms, gastric emptying testing, vagal tone, and inflammation. After enrollment, patients will undergo two upper endoscopies (pre and post therapy). Pt will be seen in clinic for recruitment, day 0, for follow-up at 4 weeks, and again at 8 weeks, for a total of six visits including their appointed endoscopy days.

### **3.2 Study Objectives**

1. Establish the effect of VNS on gastric emptying time and on cardinal symptoms of gastroparesis (nausea, vomiting, bloating, abdominal pain, and early satiety).
2. Assess the effects of VNS on various measures of quality of life, including global health and overall pain interference.
3. Investigate molecular and neuroimmune signaling pathways in different gastroparesis patients.
4. Determine the effects of VNS on measurable serum inflammatory markers and cytokines.
5. Determine the effects of VNS on measurable cytokines, nerve growth factors, and neurotransmitters in the gastric and duodenal submucosa.
6. To characterize the submucosal enteric nervous system in gastroparesis subtypes and identify novel neuro-immune interactions.
7. Determine if gastric emptying and symptom response to VNS is associated with changes in inflammatory markers and neuro-immune signaling.
8. Determine if there is a difference in response to VNS in patients with idiopathic vs. diabetic gastroparesis.
9. Evaluate the safety and tolerability of VNS therapy in patients with gastroparesis and functional dyspepsia.

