#### ***4.2 Sample size justification***

- Total of 45 patients; 15 with functional dyspepsia, 15 with diabetic gastroparesis, and 15 with idiopathic gastroparesis.
- Primary comparison: Gastric emptying half time score and GCSI, pre and post VNS
- Error protection: Type I = 0.05 two-sided and Type II = 0.10 (80% power). To detect a clinically significant change of >30% in gastric emptying time, and a reduction in  $\geq 1$  GCSI aggregate.

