6. Patients will present to endoscopy for their post-treatment upper endoscopy 4 weeks after initiation of therapy. No later than 3 days after endoscopy, patients will present to clinic at which time post-treatment gastric emptying testing, HRV testing, and laboratory tests (blood and stool) will be obtained, and the aforementioned forms will again be completed.
7. Patients will be seen in clinic again at 4 weeks after discontinuation of therapy, and undergo a repeat medical history and physical exam. At this time gastric emptying testing, HRV testing, and laboratory tests (blood and stool) will again be obtained; and the aforementioned forms will again be completed to assess whether any change in symptoms and disease severity has occurred off therapy.

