## **7. Statistical Analysis Plan**

The mean baseline GCSI aggregate score will be compared with the mean aggregate score at the end of each treatment week, and in the 4 subsequent weeks after therapy discontinuation. Paired Student T-tests will be done comparing baseline with all other subsequent time points. Gastric emptying times will be plotted before treatment, at the end of treatment, and four weeks after end of treatment and compared by ANOVA. Similarly, differences among the three subgroups of patients will be determined at baseline and after treatment.

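### Objective 1 sets out to establish the effect of VNS, but a single-arm pre-post comparison can only estimate change during VNS, and the off-therapy contrast that would help interpret it is not specified

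*Combined protocol and SAP*

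**What the plan says.** Objective 1 in section 3.2 is to "Establish the effect of VNS on gastric emptying time and on cardinal symptoms of gastroparesis". Section 3.3 words both primary endpoints, the GCSI and the breath-test emptying time, as the effect of VNS.

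Section 3.1 describes the design: "This is a prospective interventional pilot study assessing the safety and tolerability, as well as efficacy of the use of VNS". Section 4.2 gives the numbers: "Total of 45 patients; 15 with functional dyspepsia, 15 with diabetic gastroparesis, and 15 with idiopathic gastroparesis". Every patient is treated, and no sham, untreated or delayed group is described. The same section sets the main analysis: "Primary comparison: Gastric emptying half time score and GCSI, pre and post VNS".

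For GCSI, section 7 states: "Paired Student T-tests will be done comparing baseline with all other subsequent time points". The later time points are the end of each treatment week and the four weeks after stopping. Emptying times before treatment, at end of treatment and four weeks later are compared by ANOVA, with no pairwise contrast named.

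Section 5.2, item 7, brings patients back four weeks after stopping and repeats emptying, HRV, laboratory tests and forms, "to assess whether any change in symptoms and disease severity has occurred off therapy".

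**The concern.** The objective is causal and the comparison is not. GCSI is self-reported by patients who know they are treated: stimulation is raised until they feel a tug at the mouth (section 5.2, item 3). They also receive weekly calls and may use as-needed rescue medication (section 5.5). Any of these, or the natural course of the disease, can move the score without a specific VNS effect. The breath test is not self-reported, but without a concurrent control it too is open to regression to the mean and natural variation.

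The off-therapy visit carries some information on this question, because change that reverses on stopping looks different from change that persists. Seeing that requires comparing off-therapy with end-of-treatment values. Section 7 does not name that comparison for either primary endpoint, so the question put in section 5.2 has no direct test. At stake is what a positive result may be said to show.

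**Working it through.** **1. The plan's own figure.** Section 4.2 gives n=45 for a GCSI reduction of at least 1 point and an emptying change above 30%, at two-sided 0.05. It states no SD of change, so 45 cannot be reproduced. It also pairs a type II error of 0.10 with 80% power, and these disagree (0.10 means 90%). Solving the paired t-test for the SD at which a 1-point change has the stated power gives:

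| n | SD at 80% power | SD at 90% power |
|---|---|---|
| 15 | 1.29 | 1.11 |
| 45 | 2.34 | 2.02 |

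The SDs used in step 3 are therefore assumptions.

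**2. Chance of a significant pre-post test with no VNS effect.** Let d be the non-specific mean improvement divided by the SD of change; d is assumed. The paired t statistic is noncentral t with n−1 degrees of freedom and noncentrality λ = d√n. The test rejects when |t| exceeds 2.015 (n=45, √n = 6.708) or 2.145 (n=15, √n = 3.873).

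| d | λ, n=45 | P(significant), n=45 | λ, n=15 | P(significant), n=15 |
|---|---|---|---|---|
| 0.2 | 1.342 | 26% | 0.775 | 11% |
| 0.3 | 2.012 | 50% | 1.162 | 19% |
| 0.4 | 2.683 | 75% | 1.549 | 30% |
| 0.5 | 3.354 | 91% | 1.936 | 44% |

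At d = 0 the rate is 5% for both sample sizes.

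**3. What an off-therapy contrast can and cannot do.** Assume no VNS effect, a non-specific improvement of 0.5 GCSI points during treatment, n=45, and equal correlation between baseline, end of treatment and off-therapy. The simulation records how often the end-of-treatment score is significantly better than both baseline and off-therapy, each at two-sided 0.05.

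| SD of change (assumed) | Pre-post test alone | Both tests, shift persists after stopping | Both tests, shift fades fully |
|---|---|---|---|
| 1.0 | 91% | about 2 to 3% | about 84% |
| 1.29 | 72% | about 2 to 3% | about 58% |
| 2.0 | 37% | about 2% | about 22% |

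The contrast screens out a non-specific change that persists. It gives little protection against one that fades when patients knowingly stop.

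**4. Are the data for the contrast defined?**
- Emptying off therapy appears in section 5.2 (item 7), the visit schedule and section 7. Item 1 of Study Assessment and Monitoring lists only baseline and post-treatment measurements.
- The GCSI diary after VNS runs 2 weeks in the visit schedule, while section 7 uses 4 weeks.
- The GCSI diary before VNS runs 1 week in Study Assessment and Monitoring (item 2) and 2 weeks in the visit schedule.

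**The case against.** The study calls itself a pilot, and section 2 says "In this study we propose establishing proof of concept for a novel therapy for gastroparesis". An uncontrolled pre-post comparison is a common first step, and nobody reading it would mistake it for a controlled trial. This has weight: the design is defensible, and a control group is not being asked for. But proof of concept is itself a claim that the therapy works, and no passage limits how the pre-post change may be read.

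Several stronger readings are tempting, and the documents do not support them.

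- A reader might infer that non-specific improvement would usually be declared a VNS effect. That depends on a shift and an SD that are not given. The table runs from 11% to 91%, and at n=15 it stays below one half throughout. Nor does any passage make p<0.05 alone the rule for declaring an effect. Section 4.2 calls a 1-point GCSI reduction clinically significant. With a 0.5-point shift at n=45, the observed mean would reach 1 point only 0.04%, 0.5% or 4.7% of the time at SD 1.0, 1.29 or 2.0 (normal tail beyond 0.5√45/SD = 3.35, 2.60, 1.68). That is a sizing target, though, not a decision rule.
- A reader might infer that the type I error is not 5%. The paired test keeps 5% for its own null of no mean change. The difficulty is attribution.
- A reader might infer that the off-therapy data go unused or are compared only with baseline. Baseline-only holds for GCSI; the emptying ANOVA covers all three times and lacks only a named contrast.
- A reader might infer that patients enter with active symptoms, so that regression to the mean is certain. Section 4.3 requires an established diagnosis and stable medication, with no minimum GCSI, and section 4.4 excludes severe flares requiring hospitalization. Regression to the mean is possible, but its size is unknown.
- A reader of item 2 in Study Assessment and Monitoring might infer a randomised design, since it dates the baseline from randomization. Nothing else in the document describes one.

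**Conclusion.** The concern stands in limited form. The objective and primary endpoints claim an effect of VNS that a single-arm, unblinded pre-post comparison cannot isolate. That follows from the design and needs no numerical assumption. The rejection rates (26% to 91% at n=45, 11% to 44% at n=15, for shifts of 0.2 to 0.5 SD) only illustrate it, because the documents supply neither the shift nor the SD.

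The second gap is narrow: the off-therapy values are in the plan, but the comparison that answers the stated off-therapy question is not. A reader might go further and infer that reversal would establish a VNS effect. Stopping is unblinded, and under a fully fading 0.5-point placebo response both tests are passed about 22% to 84% of the time at the SDs assumed. Reversal is therefore only consistent with a VNS effect. Absence of reversal is inconclusive, since the effect may carry over and section 2 raises the possibility of disease modification.

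The pilot can go ahead; its stated conclusion and its analysis section should be changed.

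**What to change.** 1. Reword Objective 1, the two primary endpoints and any efficacy conclusion as estimating change from baseline during VNS in an uncontrolled pilot, not attributable to VNS alone.
2. Add to section 7 a prespecified paired contrast of off-therapy versus end of treatment, with a confidence interval, for GCSI and for gastric emptying. Label it supportive. State in advance that reversal is consistent with a VNS effect but may also be a fading placebo response, and that non-reversal is inconclusive. Do not make reversal a condition for calling a change VNS-related.
3. Reconcile the GCSI diary windows (after VNS, 2 versus 4 weeks; before VNS, 1 versus 2 weeks), so that the baseline mean and the off-therapy value are each defined once. Bring the list of emptying measurements in Study Assessment and Monitoring into line with section 5.2.

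The cost is one extra analysis, some rewording and a more modest conclusion. No new arm, patient or visit is needed. Which diary window applies has to be settled before the GCSI contrast can be called free.

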### **3.3 *Study Endpoints***

#### ***I. Primary Study Endpoints***

- 1.1 The primary outcome measure will be the effect of VNS on gastroparesis cardinal symptoms as measured by the gastroparesis cardinal symptom index (GCSI) questionnaire.
- 1.2 The second primary outcome measure will be the effect of VNS on gastric emptying time as measured by the gastric emptying spirulina breath test.

#### ***II. Secondary Study Endpoints***

- 2.1 The effect of VNS therapy on overall pain interference as assessed by the PROMIS pain interference questionnaire
- 2.2 The effect of VNS therapy on overall wellbeing and health as assessed by the short form 12 (SF-12).
- 2.3. The safety and tolerability of VNS in patients with gastroparesis will be assessed by recording any side effects or adverse events.
- 2.4 The effect of VNS therapy on vagal tone as assessed by heart rate variability (HRV) and respiratory variability using electrocardiogram (ASNAR) device and an HRV App called Heart Rate Variability Camera.
- 2.5 The effect of VNS therapy on systemic inflammation as measured by serum inflammatory markers and cytokines (as assessed by the Human 63-plex assay), as well as by activation markers in circulating leukocytes by flow cytometry.

2.6 The effect of VNS therapy on gastric and small intestine inflammation as measured by endoscopy biopsy tissue expression of inflammatory mediators (cytokines, chemokines, etc), and tissue infiltration of immune cells by flow cytometry and immunohistochemistry.

### ***III. Exploratory Study Endpoints***

- 3.1 Enteric neuro-immune interactions in distinct types of gastroparesis as measured by analyses of the submucosal plexus and infiltrating immune cells from endoscopy tissue biopsies via immunofluorescence, gene expression assays, and expression of neurotransmitters, nerve growth factors, cytokine receptors, and trafficking receptors.
- 3.2 Dysbiosis and bile acid metabolism in distinct types of gastroparesis as measured by stool sample 16S rRNA microbiome sequencing and metabolomics.
- 3.3 Assess the effect of VNS on neuro-immune interactions and dysbiosis in gastroparesis patients as measured in 3.1 and 3.2.

#### ***3.4 Study Duration***

1. Up to 8 weeks for screening period and baseline measures
2. Four weeks of active VNS therapy
3. Four weeks follow up period following discontinuation of therapy

### **4 Subject Selection and Withdrawal**

#### ***4.1 Study Population***

Adult patients, age 21 to 65 years old, with diagnosed functional dyspepsia, diabetic or idiopathic gastroparesis.

#### ***4.2 Sample size justification***

- Total of 45 patients; 15 with functional dyspepsia, 15 with diabetic gastroparesis, and 15 with idiopathic gastroparesis.
- Primary comparison: Gastric emptying half time score and GCSI, pre and post VNS
- Error protection: Type I = 0.05 two-sided and Type II = 0.10 (80% power). To detect a clinically significant change of >30% in gastric emptying time, and a reduction in  $\geq 1$  GCSI aggregate.

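### The sample size section equates a Type II error of 0.10 with 80% power; the two figures contradict each other and the documents do not show which was meant

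*Combined protocol and SAP*

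**What the plan says.** Section 4.2 gives the error rates as "Type I = 0.05 two-sided and Type II = 0.10 (80% power", closing the bracket there. The comparison they apply to is "Primary comparison: Gastric emptying half time score and GCSI, pre and post VNS". The target effects are a change of more than 30% in gastric emptying time and a fall of at least 1 in the aggregate GCSI score. The section lists 45 patients, 15 in each of three diagnostic groups.

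Section 3.1 repeats the numbers ("We plan to recruit a total of 45 patients, 15 patients of each subgroup") and describes the design: "This is a prospective interventional pilot study".

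For the GCSI, section 7 (Statistical Analysis Plan) says: "Paired Student T-tests will be done comparing baseline with all other subsequent time points". Gastric emptying times are to be plotted before treatment, at its end and "four weeks after end of treatment and compared by ANOVA". Section 7 gives no power, Type II error or measure of variability. Section 4.2 is the only place where power is mentioned.

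**The concern.** The phrase "Type II = 0.10 (80% power" presents two figures as the same quantity, and they are not. A Type II error of 0.10 and a power of 80% describe different designs. The sentence is complete in the current text, so the conflict does not come from a redaction or a broken table.

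This is the only power statement for the two primary endpoints in section 3.3. Someone weighing a null result could read it as a 10% or a 20% chance of having missed the target effect. Nor can anyone check 45, or 15 per group, against it: the SD of change, the formula and the powered sample are all absent.

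**Working it through.** **1. The stated pair.** Power = 1 − Type II error.

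- From 0.10: 1 − 0.10 = 0.90, not 0.80.
- From 80%: 1 − 0.80 = 0.20, not 0.10.

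The stated power is therefore not reproduced from the stated Type II error; the gap is 10 percentage points.

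**2. Does sidedness reconcile them?** No. A paired design with exactly 80% two-sided power at 0.05 has 88.8% one-sided power with 15 patients and 88.0% with 45. Neither is 90%, and the text says "Type I = 0.05 two-sided".

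**3. Does the sample size show which was meant?** The inputs from section 4.2 are two-sided alpha 0.05, N = 45 or 15, and a 1-point GCSI change; section 7 supplies the paired t-test. Power comes from the noncentral t distribution with N − 1 degrees of freedom and noncentrality d√N, where d = mean change / SD of change. Solving for d, the largest SD compatible with a 1-point change is 1/d.

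| N | Power | Detectable d | Largest SD of change |
|---|---|---|---|
| 45 | 80% | 0.427 | 2.34 |
| 45 | 90% | 0.494 | 2.02 |
| 15 | 80% | 0.778 | 1.285 |
| 15 | 90% | 0.901 | 1.11 |

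Each combination works for some SD. As the documents give no SD, N does not identify the intended power.

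**4. Size of the discrepancy in patients.** Under the normal approximation, the ratio of sample sizes at the same effect and SD is ((1.960 + 1.282) / (1.960 + 0.842))² = 1.34. With the exact t calculation, holding d at the value in the table:

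- If N was computed for 80%, then 90% needs 60 instead of 45, or 20 instead of 15.
- If N was computed for 90%, then 80% needs 35 instead of 45, or 12 instead of 15.

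**5. Sensitivity to the missing SD.** The SDs below are assumptions, not figures from the documents. They show only how strongly the answer depends on the missing input (paired t-test, 1-point GCSI change, two-sided 0.05).

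| Assumed SD of change | Power, N = 15 | Power, N = 45 | N for 80% (90%) |
|---|---|---|---|
| 1.0 | 95% | >99% | 10 (13) |
| 1.5 | 67% | 99% | 20 (26) |
| 2.0 | 44% | 91% | 34 (44) |
| 2.5 | 30% | 75% | 52 (68) |

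**6. Gastric emptying.** Power for the planned analysis cannot be worked out. Section 7 plans an ANOVA over three time points, and the documents give no SD, baseline mean or correlation between visits.

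**The case against.** **Both figures could stand under a joint-power reading.** With a Type II error of 0.10 for each primary endpoint, the chance of detecting both effects is 0.9 × 0.9 = 0.81 if the endpoints are independent, and at least 1 − 0.10 − 0.10 = 0.80 in any case. The arithmetic works, but the documents state no rule that both endpoints must succeed, and the parenthesis offers the two numbers as equivalents. If this was the intention, section 4.2 still needs rewriting to say so.

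**The missing SD and powered sample are a separate matter.** They are an incomplete justification rather than an error, and a pilot need not carry a full one. That is fair. They belong here because they are why the contradiction cannot be resolved from the text.

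**The assumed SDs may suggest a shortfall.** The range has no source in the documents, which also do not state the scale of the GCSI aggregate. This stands as a caution: the second table illustrates dependence on the SD and is not evidence that N is too small.

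**Gastric emptying could be treated in the same way.** If a 30% change were tested by a paired t-test on percentage change, the largest SD would be 70.3 (80%) or 60.7 (90%) percentage points with 45 patients, and 38.6 or 33.3 with 15. That is not the analysis in section 7, so these figures do not describe the planned test.

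**The consequence is modest.** In a single-arm pilot, a confidence interval for the observed change tells the reader more about a null result than planned power does. This limits the weight of the point but does not remove the contradiction.

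**Conclusion.** The concern holds. Section 4.2 is wrong as written: it equates a Type II error of 0.10 with 80% power, and the intended figure cannot be recovered from the documents. The discrepancy is a factor of two in the stated risk of missing the target effect, equivalent to about 1.34 times the sample size at the same effect and SD.

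The contradiction itself needs no assumption. The detectable changes and converted sample sizes rest on a paired t-test at two-sided 0.05 with complete data. The power figures by SD rest on assumed values as well. Underpowering is not shown.

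This should be corrected. It is of moderate weight, because the study is a pilot and no endpoint, test or procedure depends on the correction.

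**What to change.** Restate section 4.2 from the sponsor's own calculation, with one consistent pair and the inputs needed to check it:

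> Two-sided Type I error 0.05; Type II error [0.20, i.e. 80% power / 0.10, i.e. 90% power]. Calculated for the pre/post comparison in [all 45 patients / each group of 15], assuming an SD of change of [x] for the GCSI and [y] for gastric emptying half time.

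If joint power over both endpoints was intended, say so and give the rule. If no calculation exists, withdraw the power claim and write instead:

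> The sample size is fixed for a pilot study. With a paired t-test at two-sided 0.05, 45 patients detect a standardised change of about 0.43 with 80% power (0.49 with 90%), and a subgroup of 15 detects 0.78 (0.90). For a 1-point GCSI change this corresponds to an SD of change of at most about 2.34 (2.02) for 45 patients and 1.285 (1.11) for 15.

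The fallback text applies to the GCSI, for which a paired t-test is planned. It should say that no power is claimed for the gastric emptying ANOVA.

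The cost is one paragraph of protocol wording; N need not change. The drawback for the sponsor is that the restated power may be less favourable, or the formal claim may have to go.
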